Sample size estimate for local subset, to capture biomarkers of exposure We searched for prospective e-cigarette studies (controlled or not) that were NOT cessation based but reported on biomarkers, either CO or cotinine. We found only one (47) but acute decreases (within 1 month) in CO were only indirectly reported (in graph, separated by smoking group outcomes). Consistent with those data, we expect an overall decrease in CO within 1month of 35%, compared with no such decreases within the control group. A sample size of 80 in the e-cigarette local subset group (total of n=120 for the local subset who complete the baseline in-person lab visit) will have at least 80% power to detect a 35% decrease in CO (23.5ppm to 15.3ppm in the e-cigarette group vs. no change in the control group, assuming a standard deviation of 15.0 in the control group and 10.0 in the e-cigarette group (standard deviations were estimated from the interquartile ranges reported in the Polosa study (47) using standard procedures (134)). We expect no group differences in cotinine. We recognize that this technically implies a test of equivalence, and we are willing to accept up to +/-3% difference to conclude equivalence. With a local subset sample size of n=120 (40 control and 80 e-cigarette), $\alpha=0.05$, a two-sided t-test has >90% power to reject the null hypothesis that the two groups are not equivalent (1400ng/ml +/- 45ng/ml) in favor of the alternative hypothesis that the mean cotinine levels of the two groups are equivalent (assuming an expected difference in means of 0ng/ml and a common standard deviation of 70.0ng/ml) (135).

Statistical Considerations – Data Analyses

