All analyses are based on an intent-to-treat approach, and are nearly identical to analyses from our prior studies. Exploratory analysis will be performed on all outcomes, and both graphical displays and summary statistics will help determine if transformations will be needed. Any significant baseline differences between groups will be included in regression analyses described below. Missing Data: The most conservative approach for handling missing data (136) is to substitute them with baseline values, assuming outcomes have all returned to baseline, with no quit attempts made. If this assumption is incorrect, it biases the results towards the null by reducing between group differences (136). SRNT recommendations (136) suggest that when there are small amounts of missing data (< 10%) the conservative approach can be used with little bias in outcome. If missing data >10%, we will calculate results not only using this conservative method but also using methods in which missing data are imputed as described in the SRNT guidelines. We will also assess whether dropout is differential by study group. In our current and recent studies of cessation induction, this has not been the case, and we expect similar results here. Finally, though sex/gender is not an explicit focus, we are well poised, given our sample size, to address **potential sex/gender influences** on study outcomes.

Hyp 1a: Within the e-cigarette group, we hypothesize that at least 90% of smokers will try at least once, 45% will use regularly (at least 4/7 days, at any time during follow-up), 25% will use daily for ≥ 7 days (at any time during follow-up), 25%/10% will be using at least some/daily at final follow-up, and 20% will independently purchase e-cigarettes. Within the e-cigarette group (N=440), we will analyze prevalence of each definition of uptake. We will estimate each of these parameters, and the 95% confidence interval for each proportion.

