Hyp1b: Among smokers in the e-cigarette group, 40% will show a minimum of 50% reduction in cigarettes per day, and as a group, e-cigarette users will show greater decreases in cigs/day as compared to control. Reduction of cigarettes per day will be calculated based on the TLFB at baseline and 6 months for both groups, with “reducers” defined as those that reduce cigarettes per day by $\geq 50\%$. We will estimate the mean reduction, 95% confidence interval on the reduction, and the proportion of those that are considered “reducers” in both groups, the latter tested via a chi-square test with $\alpha=0.05$ two-sided significance level.

Hyp2: Within a subset of locally recruited smokers, we hypothesize that use of e-cigarettes will lead to significant decreases in CO and NNAL, but no net change in overall nicotine exposure. Changes in CO, NNAL and cotinine will be calculated based on the baseline, 1, and 6-month measurements. Mean change in CO/NNAL (thru 1 and 6 months) will be compared via a two-sample t-test with $\alpha=0.05$ significant level. In order to test equivalence for change in cotinine between the two groups, the TOST procedure (137) will be followed where two one-sided tests will be used to test that the difference in the change between groups (Δ) is within the +/-3% bounds that we are willing to accept ($H_{01}: \Delta < -3\%$; $H_{02}: \Delta < +3\%$). If Δ is contained completely within the +/-3% bounds, then equivalence will be concluded. We will use an $\alpha=0.05$ significance level.

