Hyp1b: Among smokers in the e-cigarette group, 40% will show a minimum of 50% reduction in cigarettes per day, and as a group, e-cigarette users will show greater decreases in cigs/day as compared to control. Reduction of cigarettes per day will be calculated based on the TLFB at baseline and 6 months for both groups, with “reducers” defined as those that reduce cigarettes per day by $\geq 50\%$. We will estimate the reduction, 95% confidence interval on the reduction, and the percent of those that are considered “reducers” in both groups, the latter tested via a chi-square test with an $\alpha=0.05$ two-sided significance level.

Hyp2: Within a subset of locally recruited smokers, we hypothesize that use of e-cigarettes will lead to significant decreases in CO, but no net change in overall nicotine exposure. Changes in CO and cotinine will be calculated based on the baseline, 1, and 6-month measurements. Change in CO (thru 1 and 6 months) will be compared via a two-sample t-test with $\alpha=0.05$ significant level. In order to test equivalence for change in cotinine between the two groups, the TOST procedure (137) will be followed where two one-sided tests will be used to test that the difference in the change between groups (Δ) is within the $\pm 3\%$ bounds that we are willing to accept ($H_{01}: \Delta < -3\%$; $H_{02}: \Delta < +3\%$). If Δ is contained completely within the $\pm 3\%$ bounds, then equivalence will be concluded. We will use an $\alpha=0.05$ significance level.

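### Cotinine equivalence: the stated >90% power belongs to ±45 ng/ml, not the tested ±3% (42 ng/ml, about 85%), and baseline substitution of missing values favours equivalence

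*Combined protocol and SAP*

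**What the plan says.** **Margin and power.** The section on the sample size estimate for the local subset recognises that expecting no group difference in cotinine calls for an equivalence test, and says "we are willing to accept up to +/-3% difference to conclude equivalence". It then claims that "a two-sided t-test has >90% power to reject the null hypothesis" of non-equivalence with 40 control and 80 e-cigarette participants. That claim assumes a true difference of 0 and a common SD of 70 ng/ml for mean levels. The null there is that "the two groups are not equivalent (1400ng/ml +/- 45ng/ml) in favor of the alternative hypothesis".

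**Analysis.** Under Hyp2 in Statistical Considerations – Data Analyses, and again in the Data and Safety Monitoring Plan, section 9, the purpose is to "test equivalence for change in cotinine between the two groups" by the two one-sided tests (TOST) procedure. The bounds are ±3%, and the plan adds "We will use an $\alpha=0.05$ significance level". Both places print the upper null hypothesis as a difference below +3%.

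**Missing data.** Statistical Considerations – Data Analyses opens with "All analyses are based on an intent-to-treat approach". The same paragraph describes replacing missing values with baseline values as the most conservative approach, on this ground: "If this assumption is incorrect, it biases the results towards the null by reducing between group differences". Under 10% missing, this is the only method described. Above 10%, imputed results are added to it. No exception is made for cotinine, and the plan does not say which result governs when both are reported.

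**The concern.** The absence of a net change in cotinine is the self-titration claim of Aim 2. Two things bear on it.

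First, the margin that is tested and the margin that was powered differ, so the quoted power does not describe the planned test.

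Second, the argument for baseline substitution holds only for tests of a difference. There the null is no difference, and shrinking the groups together works against the study hypothesis. In the TOST the null is that the groups differ by at least the margin. Shrinking them together then works for the study hypothesis, so missed visits make equivalence easier to declare. The rule's cited source (reference 136) is titled for dichotomous outcomes, whereas change in cotinine is continuous.

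**Working it through.** **Inputs.** From the local-subset sample size section: 80 e-cigarette and 40 control participants, SD 70 ng/ml, true difference 0, reference mean 1400 ng/ml, powered margin 45 ng/ml. From Hyp2: margin ±3%, level 0.05, read as 0.05 for each one-sided test.

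**Margin.** 0.03 × 1400 = 42 ng/ml. The powered margin is 45/1400 = 3.2%.

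**Reproducing the plan's figure.** SE = 70 × √(1/40 + 1/80) = 13.56. By the normal approximation, power = 2Φ(margin/SE − 1.645) − 1.
- At ±45: 45/13.56 = 3.32, and 2Φ(1.675) − 1 = 0.906. The exact value (118 df, integrating over the pooled variance) is 0.902. The stated >90% is reproduced.
- At 0.025 per one-sided test the exact value at ±45 is 0.817, so the plan must have used 0.05 per side.

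**At the tested margin.**
- At ±42: 42/13.56 = 3.10, and 2Φ(1.454) − 1 = 0.854. The exact value is 0.849.

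**SD of change.** The 70 is attached to levels, but the test is on change. If 70 is the level SD and ρ is the baseline-to-follow-up correlation, the SD of change is 70√(2(1 − ρ)). Exact power at ±42 is then 41% for ρ = 0, 62% for 0.25, 85% for 0.5 and 99% for 0.75. Indexed by SD of change, it is 0.98 at 55, 0.91 at 65, 0.78 at 75 and 0.63 at 85.

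**Baseline substitution.** A substituted participant has change 0. If a fraction f is missing at random in both arms and the control mean change is 0, a true difference D becomes (1 − f)D. Because n stays at 80/40, the SE shrinks as well. Take D at the margin (42), SD of change 70 and f = 10%:
- Expected difference: 0.9 × 42 = 37.8.
- Control variance: 0.9 × 4900 = 4410. E-cigarette variance: 4410 + 0.9 × 0.1 × 42² = 4569.
- SE = √(4410/40 + 4569/80) = 12.94.
- False equivalence ≈ Φ((42 − 37.8)/12.94 − 1.645) = Φ(−1.32) = 9.3%.

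Simulation with 200,000 trials per setting, under the same assumptions, gives the probability of declaring equivalence:

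| Missing | True difference 0 | True difference 42 (3%) | True difference 56 (4%) |
|---|---|---|---|
| 0% | 0.849 | 5.1% | 0.4% |
| 5% | 0.868 | 6.9% | 0.7% |
| 10% | 0.892 | 9.25% | 1.1% |
| 11% | – | 9.7% | – |

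The rise in the first column is not a real gain in power. It comes from the same shrinkage that inflates the second column. Using observed values only, false equivalence at the margin stays at 5.0% with either 5% or 10% lost.

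**Plausible missingness.** Recruitment & Retention Feasibility reports more than 95% of local visits completed in the earlier smokeless-product pilots and 89% of follow-up visits in the R21. That suggests roughly 5–11% missing.

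**The case against.** **The margin gap is close to rounding.** 3.2% against 3% is small, and 85% is still above the 80% used for abstinence and CO. No sample size changes. Cotinine is one biomarker in a 120-person subset, and uptake is the primary outcome. This limits the weight of the point, but the quoted power remains wrong for the stated margin.

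**The 85% is itself conditional.** Hyp2 names no reference mean, so 42 ng/ml is a conversion using the 1400 in the sample size section. The SD of change is not given either, and the 41–99% range shows that this matters more than the 3 ng/ml. Both points stand. They are reasons to show power over a range, not to keep the >90%.

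**The missing-data rule may not have cotinine in view.** Its wording refers to quit attempts, its source concerns dichotomous outcomes, and below 10% missing the text permits the approach rather than requiring it. Even so, no alternative is given for cotinine.

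**The direction of bias depends on the scenario.** If both arms fell by 100 ng/ml and 10% were missing, substitution would lower power from 0.85 to 0.81. With true changes of −92 (e-cigarette, 5% missing) and −50 (control, 10% missing), false equivalence is about 4.4%, slightly below nominal. These figures are correct, but they need a large shared decline or differential dropout. The plan expects no net cotinine change and no differential dropout. If dropouts really did return to baseline, substitution would add no error.

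**The retention precedent is soft.** The two pilots behind the >95% lasted two weeks each (Data and Safety Monitoring Plan, section 11). Missingness at 1 and 6 months could differ from the range used here.

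**Conclusion.** Both parts hold, and the point should be fixed, although neither effect is large.

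The >90% power belongs to ±45 ng/ml. At ±3% of 1400 ng/ml it is about 85%, a drop of about 5 points, given SD 70, 80/40 participants, true difference 0 and 0.05 per one-sided test.

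Baseline substitution is anti-conservative for this test under the plan's own expectations. With a true difference exactly at the margin, the 5% error becomes about 7% at 5% missing and about 9% at 10%. This assumes an SD of change of 70, no mean change in controls and equal, completely random missingness. For a true difference of 4%, false equivalence stays near 1%.

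The printed upper null is a sign slip whose intent is clear. The reference to a two-sided t-test should be reconciled with the two one-sided tests.

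**What to change.** 1. State one margin, in percent and in ng/ml, with its reference mean. If ±3% is kept, give power as about 85% under SD 70, and show it across SDs of cotinine change (0.98, 0.91, 0.78 and 0.63 at 55, 65, 75 and 85).
2. For cotinine, make a likelihood-based repeated-measures model or multiple imputation the main analysis at any level of missingness, and keep baseline substitution as a sensitivity analysis. An observed-only approximation puts power at ±42 at about 83% with 5% lost (76/38 analysed) and 80% with 10% lost (72/36).
3. In both statements of Hyp2, write the nulls as Δ ≤ −3% and Δ ≥ +3%. State that equivalence requires the 90% confidence interval for Δ to lie wholly within the margin, and align the sample size section's description of the test.

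The cost is SAP wording, a less favourable quoted power and a little more analysis. No extra participants or assays are needed.

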suggesting: a) strong initial uptake of e-cigarette, b) favorable liking/satisfaction/withdrawal relief, and c) that these effects are not nicotine specific (few differences between active vs. placebo). We also just completed a R21 that is thematically very similar to the current trial: 68 participants randomized to receive e-cigarettes (again, BluCig) or not, with a naturalistic sampling period and prospective follow-up. The R21 used ecological momentary assessment (EMA) methods to capture uptake patterns among smokers who are provided an e-cigarette. The study included a control group (Total N=68) that allows us to compare prospective changes in smoking behavior as compared to smokers who do not receive an e-cigarette (BluCig). Manuscript is in preparation and results are to be presented at SRNT 2017. Figure 1 shows uptake and amount of usage of e-cigarettes, during and following the sampling period. General uptake during the 3-wk sampling period was strong: 100% of those receiving BluCig used at least once, 71% reported regular use during at least 1 of the 3 sampling weeks, and 63% used daily during at least 1 week. Smokers in the e-cigarette group were 2.9x more likely (41 vs. 14%) to independently purchase their own e-cigarette, 1.6x more likely (44% vs. 27%) to make a quit attempt, and 3x more likely (15% vs. 5%) to achieve “floating abstinence” (any 7-day period of non-smoking, ever within study). Cessation-related outcomes were non-significant for this small study, and we caution against over-interpretation since confidence intervals (not shown here) are wide. We found significant reductions in both CPD and CO/NNAL, but no changes in cotinine. EMA data suggested clear contextual differences for e- vs. conventional cigarettes. EMA compliance was strong: 80% of participants completed at least 12 diaries in 3 weeks (most comparable to herein) and 78% completed at least 3 diaries/week. These early results show: a) general congruence of outcomes to those we hypothesize for the proposed larger trial, b) palatability of product, c) uptake/use even without structured instructions to do so, and d) our strong experience in methods: recruitment, sampling product, EMA, biomarkers, and product evaluation. The general methods and measures from these studies guide our current trial, though we now turn to a 2nd generation device, which should have even fewer barriers to uptake and/or substitution.

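### The >90% power for cotinine equivalence rests on an unexplained SD of 70 ng/ml (5% of the mean). It is 85% at the plan's own ±3% bounds and all but gone once the SD reaches about 131–140 ng/ml

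*Combined protocol and SAP*

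**What the plan says.** The section on the sample size for the local subset plans the cotinine comparison as follows: "With a local subset sample size of n=120 (40 control and 80 e-cigarette" participants), "a two-sided t-test has >90% power to reject the null hypothesis that the two groups are not equivalent", with an equivalence zone written as "1400ng/ml +/- 45ng/ml" and "assuming an expected difference in means of 0ng/ml and a common standard deviation of 70.0ng/ml". The only support for these inputs is a reference number, which points to a published comparison of nicotine biomarkers. The wording concerns mean levels in the two groups. Nothing says whether 70 ng/ml is the SD of a level or of a change, and no other SD is tried.

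The Hyp 2 analysis (Statistical Considerations – Data Analyses, repeated in the Data Analysis Plan of the monitoring section) is on change: "two one-sided tests will be used to test that the difference in the change between groups" lies inside ±3% bounds, and "We will use an $\alpha=0.05$ significance level". Changes are taken at 1 and 6 months.

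The same sample size section plans carbon monoxide (CO) for this subset "assuming a standard deviation of 15.0 in the control group and 10.0 in the e-cigarette group", on means of 23.5 ppm and, after e-cigarette use, 15.3 ppm. Those SDs were derived from interquartile ranges in a different cited cohort. For the sponsor's R21 pilot, the preliminary data section reports: "We found significant reductions in both CPD and CO/NNAL, but no changes in cotinine". It gives no SD.

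**The concern.** An equivalence test with a fixed narrow margin depends almost entirely on the SD. Here the SD is 5% of the mean, in a trial that admits anyone smoking 5 or more cigarettes a day with no upper limit and expects some participants to quit, some to halve their smoking and some to barely use the product. If the SD of the analysed quantity is even twice the planned value, the 90% confidence interval is about as wide as the equivalence zone when the two arms are truly identical.

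Unchanged cotinine is half of Hyp 2 and the direct evidence for Aim 2's self-titration question. With too small a planning SD, the likely result is an inconclusive test, followed by pressure to read a non-significant difference as equivalence. The sample size section itself recognises that the hypothesis calls for an equivalence test.

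**Working it through.** **Inputs from the plan:** n = 40 and 80; mean 1400 ng/ml; true difference 0; SD 70; margin ±45 (power paragraph) or ±3% (power paragraph and Hyp 2 analysis). I read ±3% as 0.03 × 1400 = 42 ng/ml; 45/1400 is 3.2%. Alpha is 0.05 for each one-sided test.

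**Reproducing the stated power.** SE = 70 × √(1/40 + 1/80) = 70 × 0.1936 = 13.56. Normal approximation: 2Φ(margin/SE − 1.645) − 1.
- Margin 45: 2Φ(3.320 − 1.645) − 1 = 90.6%. The exact value (t with 118 df, integrated over the sample SD) is 90.2%. The stated figure is reproduced.
- Margin 42: 2Φ(3.099 − 1.645) − 1 = 85.4%; exact 84.9%. The stated figure is not reached at the bounds that will be tested.

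With 0.025 per side, exact power would be 81.7% at ±45 and 73.4% at ±42, so the plan evidently used 0.05 per side.

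**Varying the SD (exact power, true difference 0):**

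| SD (ng/ml) | CV | Power, ±42 | Power, ±45 | 90% CI half-width |
|---|---|---|---|---|
| 70 | 5.0% | 84.9% | 90.2% | 22.5 |
| 80 | 5.7% | 70.7% | 78.6% | 25.7 |
| 100 | 7.1% | 39.1% | 49.4% | 32.1 |
| 120 | 8.6% | 12.4% | 22.1% | 38.5 |
| 140 | 10.0% | 0.7% | 3.6% | 44.9 |
| 150 | 10.7% | 0.1% | 0.7% | 48.2 |
| 420 | 30% | 0 | 0 | 134.8 |

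The half-width equals the margin at SD = 42/(1.658 × 0.1936) = 131 for ±42, and at 45/(1.658 × 0.1936) = 140 for ±45. These thresholds apply to whichever SD enters the test, of level or of change.

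**Comparing SD 70 with the plan's other assumptions.**

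1. *CO as a benchmark.* 15/23.5 = 63.8%; 10/23.5 = 42.6%; on the post-switch mean, 10/15.3 = 65.4%. Planning CVs for CO are therefore roughly 43–65%, against 5% for cotinine.

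2. *If 70 is an SD of change.* With equal variances, SD of change = SD of level × √(2(1 − ρ)), so ρ = 1 − 70²/(2 × SD²). An assumed level CV of 30% (SD 420) needs ρ = 0.986. CO-like CVs of 43–64% (SD 596–894) need 0.993–0.997. Holding the SD of change to 140 would still need 0.944 at SD 420 and 0.972–0.988 at the CO-like CVs.

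3. *Quitting.* The trial is powered on 8% abstinence in controls at 6 months. Suppose everyone else's cotinine is unchanged and quitters fall by a fraction f of 1400. The SD of change is then f × 1400 × √(0.08 × 0.92) = f × 380: about 380 ng/ml for a full fall and 190 for a fall by half. To stay at 140, f would have to be no more than 140/380 = 37%.

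4. *If that spread applies to controls only* and the e-cigarette arm keeps SD 70, the SE is √(190²/40 + 70²/80) = 31.0 for a fall by half, giving a half-width of 1.645 × 31.0 = 51 ng/ml. For a full fall, √(380²/40 + 70²/80) = 60.6 gives about 100 ng/ml. Both exceed either margin.

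**The case against.** The arithmetic in the plan is right on its own inputs, and those inputs carry a citation that cannot be checked here. CO and cotinine are different markers, one in breath and one in urine, and their planning SDs come from different sources. The CO figures were not measured in the people to be enrolled, and nothing in the documents says the two CVs should agree. The planned test is on change, which removes stable differences between people, so the wide entry criterion says less about the relevant SD than it first appears to. The analysis section also leaves room for a transformation. Finally, too small an SD leads to an inconclusive test and not to a false claim, in one component of Aim 2.

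Most of this stands as a limit on what can be said. The CO comparison prompts the question and does not settle it. A reader might infer that 70 is a mislabelled standard error or a unit slip; no passage supports either explanation. A reader might also infer that equivalence can never be concluded whatever the truth; that holds only above the thresholds shown, and at SD 100 power is still 39–49%.

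What does not answer the point is the appeal to change. The quitting calculation is itself about change and uses the plan's own quit rate. The general allowance for transformations leaves the ±3% bounds as they are, and a log scale does not remove the variation that quitters introduce.

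**Conclusion.** The stated >90% power should not be relied on. At the ±3% bounds to be tested it is 85% with the plan's own SD. It falls to 39% (±42) or 49% (±45) at SD 100, and to about 1% or 4% at SD 140. The interval cannot be expected to fit inside the zone once the SD exceeds about 131 or 140 ng/ml.

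The true SD is unknown from the documents, so this is a finding of an unsupported and fragile assumption, not proof of an error. For the 6-month comparison the case is stronger. The 8% control quit rate implies an SD of change of about 190–380 ng/ml, assuming quitters' cotinine falls by half to fully and nobody else changes. If so, equivalence is essentially unreachable. For the 1-month comparison the documents give no quit rate, and the doubt rests on the entry criterion and the CO benchmark alone.

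The point affects the cotinine part of Hyp 2. It does not touch the primary uptake outcome or the power for abstinence.

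**What to change.** 1. State whether 70 ng/ml is the SD of a level or of a change, and how it was obtained from the cited source.
2. Replace it with the SD of change, or the residual SD after adjustment for baseline, from the R21 pilot if that is available. The documents confirm that cotinine was measured there but report no SD, and the pilot used a different device.
3. Restate the power of the two one-sided tests at the ±3% margin, separately for 1 and 6 months, over a range of SDs. Use one margin throughout.
4. If power is near zero, choose one of two courses before anyone sees cotinine by arm. Either report the cotinine part of Hyp 2 as an estimate (ratio of geometric means adjusted for baseline, with 90% and 95% confidence intervals), or adopt a log-scale margin. Such a margin must be justified by what difference in nicotine exposure is scientifically unimportant, and not chosen because 120 people can support it.

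The cost is one recalculation, a less favourable stated power and a softer cotinine claim. No extra participants or samples are needed.

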Our primary focus in this study is the short and long term behavioral impact of e-cigarettes. We considered a trial that was powered on e-cigarette uptake or substitution of conventional cigarettes (Specific Aim 1). These questions alone are important outcomes that would inform the public health debate. However, it would be a missed opportunity to not ask about overall exposure (Specific Aim 2) and quitting (Specific Aim 3). We also believe that, if group differences in quitting do exist, it would be entirely shortsighted if we lacked sensitivity (i.e., power) to demonstrate them. So while we focus on uptake, adoption, and patterns of dual use, we power our study on the most stringent outcome: point prevalence abstinence at 6 months (continuous abstinence is more stringent, but inappropriate here since there is no quit date to commence cessation). Table 4 depicts various sample size scenarios, under the guiding belief that e-cigarettes will facilitate quitting (see Intro). These scenarios are all based on proposed 2:1 randomization, in an effort to have better precision (i.e., tighter confidence intervals) for our primary outcome, involving only the e-cigarette group. Our base rates for quitting come from our three prior/ongoing nationwide studies, in which 6-month abstinence rates within control group ranged 4-13% (75, 76). We also recognize other population estimates (~5%) of population-based quitting (133), and ultimately take an estimate within this range: 8%. As for quit rates in the e-cigarette group, we note outcomes from most relevant study yet published: an uncontrolled observational cohort (i.e., naturalistic) study of smokers given e-cigarettes for up to 6 months (47), in which 23% (ITT, based on full N) and 33-39% (respondent only analyses) were quit at 6 months. We think that is a bit high. Given that we provide e-cigarettes for only ~1month, we expect somewhat lower rates of quitting. We power on a RR of 2.0: 8% vs. 16%. We would like to detect even smaller increases in quit rates (5% vs. 10%; RR still 2.0), but clearly that is not feasible. We thus decide on 600 participants, but inflate this by 10% to account for attrition: 660 participants to be enrolled

Table 4: Sample Size Needs

		Quit Rate in E-Cigarette Group				
		10%	15%	16%	20%	25%
Quit Rate in Control Group	5%	1015	332	287	179	117
	8%	7324	755	600	305	174
	10%		1576	1135	463	233
	15%				2067	2486

2:1 randomization (e cig:control); 80% power

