Hyp 3: Provision and use of e-cigarettes will lead to increased incidence of (Hyp3a) quit attempts, (Hyp 3b) cessation, and (Hyp 3c) motivation/confidence to quit. Logistic regression analyses will be performed with (1) any quit attempt within 6 months (1=one or more quit attempts, 0=none), (2) any 24hr quit attempt (1=one or more 24 hour quit attempt, 0=none), (3) point prevalence abstinence at 6 months (1=7 day abstinence at 6 month call, 0=not abstinent), and (4) floating abstinence (1=any 7 day period of abstinence during study, 0=no abstinence) as the outcomes and group (e-cigarette vs. control) as the covariate. The coefficient on group provides a log odds ratio for measuring the increased odds of (1) any self-defined quit attempts, (2) 24hr quit attempts, (3) point prevalence abstinence, and (4) floating abstinence in the e-cigarette group compared to the control group. Statistical significance of these coefficients will be assessed using a p-value with a two-sided alpha of 0.05, and both the odds ratio and its 95% confidence interval (CI) will be reported. Motivation and confidence to quit are evaluated on a continuous scale (0-10), and linear regression models will be used with motivation/confidence to quit at 6 months as the outcomes with group (e-cigarette vs. control) as the covariate (along with baseline motivation/confidence and any other variables that are different between groups at baseline treated as covariates). Secondary analyses will include regression analyses where number of quit attempts are compared across groups using poisson or linear regression (depending on the distribution of number of quit attempts). We will also repeat this analysis: a) based on those who do vs. do not use e-cigarettes, and b) using quit attempts and abstinence of all tobacco products, including e-cigarettes.

10. Quality Assurance Plan

The REDCap system has validation options to not accept outliers, illogical response patterns, etc. The PI will have weekly meetings with the research assistants to discuss qualitative comments received during data collection and any problems in data collection. The statistician will periodically examine the database to look for irregularities. Initial data analyses will examine distributions of variable scores, comparability of baseline characteristics, follow-up rates and use of extra-study cessation treatment across conditions in case analyses need to be adjusted for these.

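### Baseline substitution biases toward the null only when dropout is similar in both arms; with unequal dropout it can create or distort differences, and nothing in the plan then triggers imputation

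*Combined protocol and SAP*

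**What the plan says.** The rule is in Statistical Considerations – Data Analyses, under Missing Data. The approach described as most conservative is to "substitute them with baseline values, assuming outcomes have all returned to baseline, with no quit attempts made". On its direction of error the text states: "If this assumption is incorrect, it biases the results towards the null by reducing between group differences".

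A second method comes in at a threshold: "If missing data >10%, we will calculate results not only using this conservative method but also using methods in which missing data are imputed". The threshold names neither arm, nor does it say how missingness is counted across outcomes and visits.

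On imbalance the section says "We will also assess whether dropout is differential by study group", and continues: "In our current and recent studies of cessation induction, this has not been the case, and we expect similar results here". It names no analysis to follow if dropout does differ. Separately, the Data and Safety Monitoring Plan, section 10 (Quality Assurance Plan), has initial analyses look at "follow-up rates and use of extra-study cessation treatment across conditions in case analyses need to be adjusted for these". Neither the adjustment nor the condition for making it is defined.

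**The concern.** Substitution counts every missing participant as not abstinent, not a reducer and without a quit attempt. If some of them did quit or cut down, the arm that loses more people loses more true events. With equal losses the arms shrink together and the plan's sentence is right. With unequal losses, the gap between arms reflects retention as well as behaviour.

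The trial is open and only one arm receives product, so unequal retention is possible. Under 2:1 allocation, the larger arm can hold the overall figure below 10% while the smaller arm is well above it. In that case substitution is the only method described.

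At stake are the between-arm comparisons in Hyp1b and Hyp 3. The question of whether e-cigarettes undermine quitting is also affected, because a method that pulls results toward no difference is not the cautious choice there.

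**Working it through.** **Inputs from the plan.** Arms of 440 and 220; two-sided 5% chi-square test; design rates of 16% versus 8% for 6-month abstinence; a detectable decrement of 4% versus 8% (all from Sample Size & Power). A 40% reducer rate (Hyp1b, hypothesised for the e-cigarette arm). A 27% quit-attempt rate (control arm of the completed pilot, Ongoing / Recent studies of e-cigarettes).

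**Assumptions.** Per-arm dropout is not given in the documents, so the values below are illustrative. Dropouts are taken to have the same true event rate as completers in their arm. To model no effect, the 40% and 27% rates are set equal in both arms. Error rates and power for 440 versus 220 come from full binomial enumeration of the Pearson test.

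**1. The plan's own figure.** Let the mean rate be (2×0.16 + 0.08)/3 = 0.133. Control n = [1.96√(1.5×0.133×0.867) + 0.842√(0.16×0.84/2 + 0.08×0.92)]² / 0.08² ≈ 200.2, rounded up to 201. The total is 3×201 = 603, against 600 stated, so the figure reproduces. Then 600×1.10 = 660.

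**2. Effect of substitution.** Observed rate = p(1 − d), where d is the arm's missing fraction. With no true effect, the expected false difference is p × (d_control − d_ecig). Overall missingness is (2×d_ecig + d_control)/3.

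**3. Design alternative, 16% versus 8%.**

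| Dropout, e-cig vs control | Overall | Observed rates | Difference | RR | Power |
|---|---|---|---|---|---|
| none | 0% | 16.0 vs 8.0% | 8.0 points | 2.00 | 84.5% |
| 10% vs 10% | 10.0% | 14.4 vs 7.2% | 7.2 points | 2.00 | 79.8% |
| 5% vs 15% | 8.3% | 15.2 vs 6.8% | 8.4 points | 2.24 | 90.4% |
| 12% vs 5% | 9.7% | 14.1 vs 7.6% | 6.5 points | 1.85 | 70.4% |

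Equal dropout moves the difference toward the null, as the plan says. The 5% versus 15% row moves it away from the null.

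**4. No true effect: type I error.**

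| Outcome, common true rate | 10% vs 10% | 5% vs 15% | 12% vs 5% | 7% vs 12% |
|---|---|---|---|---|
| Abstinence at 6 months, 8% | 5% | 6% | 6% | 5% |
| Quit attempts, 27%, all dropouts' attempts lost | 5% | 11% | 9% | 6.5% |
| Reducers at 6 months, 40% | 5% | 17% | 11% | 8% |

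At 5% versus 15%, the observed reducer rates are 40%×0.95 = 38.0% and 40%×0.85 = 34.0%. Overall missingness in the 7% versus 12% column is (14 + 12)/3 = 8.7%. No column exceeds 10% overall, so none triggers imputation.

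**5. Quit attempts are cumulative.** Attempts are collected over repeated calls, so one reported before loss still counts, and the 11% above is an upper figure for that scenario. If half of dropouts' attempts were recorded before loss, observed rates are 27%×(1 − 0.025) = 26.3% and 27%×(1 − 0.075) = 25.0%. The type I error is then about 6.5%.

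**6. Detecting a decrement.** For a true 4% versus 8%, 5% versus 15% dropout gives 4%×0.95 = 3.8% and 8%×0.85 = 6.8%. Power falls from 58% with complete data to 41%.

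**The case against.** The best defence is that the plan anticipates the problem and expects it not to arise. It will compare dropout between arms, reports none of concern in the team's related studies, and allows for adjustment in the Quality Assurance Plan. The Control Group section gives controls extra reimbursement to offset the free product. Call completion in earlier trials was 88–95% (Table 2) and the pilot completed 89% of follow-up visits, so missingness could well exceed 10% and bring in imputation anyway. The outcome on which the trial is powered barely moves. The uptake estimates in Hyp 1a are made within one arm, so unequal dropout cannot create a false arm difference there.

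Most of this stands and limits the size of the point. It does not rescue the unconditional sentence, and neither check activates the imputation analysis.

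Three stronger readings go too far:

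- A reader might infer false-positive rates of 17% or even 33% for quit attempts. Those need a 40% base rate, dropout of 5% versus 15% or 5% versus 20%, and the loss of every dropout's attempts. The pilot control rate is 27%, and attempts are recorded over repeated calls.
- A reader might infer that the plan has no response at all to unequal follow-up. It has one, left undefined.
- A reader might infer that the plan would take a null result as evidence of no harm. It says no such thing: tests are two-sided, and the monitoring board reviews any shortfall in quitting.

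**Conclusion.** The point holds in limited form. The toward-the-null statement is correct for similar dropout and wrong as a general claim, and the 10% trigger does not respond to imbalance. The consequence is small for 6-month abstinence (about 6% type I error at 5% versus 15% dropout) and modest for cumulative quit attempts (between about 6.5% and 11%). It is material for the reducer comparison (about 17%). With a milder 7% versus 12% split, all three lie between 5% and 8%. Substitution is also not conservative for detecting reduced quitting, as the loss of power for the plan's own decrement shows.

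This rests on assumed dropout rates that the plan does not expect, and on dropouts behaving like completers in their arm. If every dropout has truly returned to baseline, substitution causes no bias, however unequal the losses.

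**What to change.** In Statistical Considerations – Data Analyses, report the planned imputation analysis beside baseline substitution in all cases. At minimum, trigger it when either arm exceeds 10% missing or when dropout differs by arm, and say how missingness is counted. Qualify the direction-of-bias sentence so that it applies only when dropout is similar between arms. Add that substitution is not conservative for detecting reduced quitting. State in the Quality Assurance Plan that this analysis is the response to unequal follow-up.

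The cost is a few lines of text and one extra run of an analysis already specified. Enrolment and data collection do not change.
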